10.1. Sample Size Determination

Up to 42 subjects may be enrolled in order that 24 subjects complete the study.

For rosuvastatin AUC, the intrasubject variability (coefficient of variation) was estimated to be 25.5% by assuming intrasubject variability comprised half of the total variability of 51% (CDER 2003); Martin et al. (2016) estimated the intrasubject variability of rosuvastatin AUC to be 21%. A sample size of 24 subjects will provide 92.3% probability that the estimated AUC geometric mean ratio will be within 0.15 of the upper and lower bounds of the 90% confidence interval (CI) in the log scale, which corresponds to approximately 0.162 in the natural scale.

While this study is not powered for the C_{max} geometric mean ratio to be within 0.15 of the upper and lower bounds of the 90% CI in the log scale, the C_{max} power calculations are described here to give the expected results context. For rosuvastatin C_{max} , the intrasubject variability was estimated to be 35.9% by assuming intrasubject variability comprised half of the total variability of 71.8% (CDER 2003); Martin et al. (2016) estimated the C_{max} intrasubject variability of rosuvastatin to be 34%. A sample size of 24 subjects will provide 19.6% probability that the estimated C_{max} geometric mean ratio will be within 0.15 of the upper and lower bounds of the 90% CI in the log scale.

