7. SAMPLE SIZE JUSTIFICATION

Up to 28 subjects may be enrolled in order that 24 subjects complete the study.

For rosuvastatin area under the concentration curve (AUC), the intrasubject variability (coefficient of variation [CV%]) was estimated to be 25.5% by assuming intrasubject variability comprised half of the total variability of 51% (CDER 2003); Martin et al. (2016) estimated the intrasubject variability of rosuvastatin AUC to be 21%. A sample size of 24 subjects will

provide 92.3% probability that the estimated AUC geometric mean ratio will be within 0.15 of the upper and lower bounds of the 90% confidence interval (CI) in the log scale, which corresponds to approximately 0.162 in the natural scale.

While this study is not powered for the maximum observed drug concentration (C_{max}) geometric mean ratio to be within 0.15 of the upper and lower bounds of the 90% CI in the log scale, the C_{max} power calculations are described here to give the expected results context. For rosuvastatin C_{max} , the intrasubject variability was estimated to be 35.9% by assuming intrasubject variability comprised half of the total variability of 71.8% (CDER 2003); Martin et al. (2016) estimated the C_{max} intrasubject variability of rosuvastatin to be 34%. A sample size of 24 subjects will provide 19.6% probability that the estimated C_{max} geometric mean ratio will be within 0.15 of the upper and lower bounds of the 90% CI in the log scale.

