Application of this procedure to all PK analyses is not a requirement. Rather, this procedure provides justification for exclusion of data when scientifically appropriate. This procedure describes the methodology for identifying an individual value as an outlier for potential exclusion, but does not require that the value be excluded from analysis. The following methodology will not be used to exclude complete profiles from analysis.

Data within an Individual Profile

A value within an individual profile may be excluded from analysis if any of the following criteria are met:

- For PK profiles during multiple dosing, the concentration of the pre-dose sample exceeds all measured concentrations for that individual in the subsequent post-dose samples.
- For PK profiles during single dosing of non-endogenous compounds, the concentration in a pre-dose sample is quantifiable.
- For any questionable datum that does not satisfy the above criteria, the profile will be evaluated and results reported with and without the suspected datum.

Data between Individual Profiles

1. If $n < 6$, then the dataset is too small to conduct a reliable range test. Data will be analyzed with and without the atypical value, and both sets of results will be reported.
2. If $n \geq 6$, then an objective outlier test will be used to compare the atypical value to other values included in that calculation:
 - a. Transform all values in the calculation to the logarithmic domain.
 - b. Find the most extreme value from the arithmetic mean of the log transformed values and exclude that value from the dataset.
 - c. Calculate the lower and upper bounds of the range defined by the arithmetic mean $\pm 3 \times SD$ of the remaining log-transformed values.

- d. If the extreme value is within the range of arithmetic mean $\pm 3 \times \text{SD}$, then it is not an outlier and will be retained in the dataset.
- e. If the extreme value is outside the range of arithmetic mean $\pm 3 \times \text{SD}$, then it is an outlier and will be excluded from analysis.

If the remaining dataset contains another atypical datum suspected to be an outlier and $n \geq 6$ following the exclusion, then repeat step 2 above. This evaluation may be repeated as many times as necessary, excluding only one suspected outlier in each iteration, until all data remaining in the dataset fall within the range of arithmetic mean $\pm 3 \times \text{SD}$ of the log-transformed values.

Reporting of Excluded Values

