9.3.2 Pharmacokinetic Statistical Inference

Rosuvastatin administered alone (Period 1 Day 1) will represent the reference treatment and rosuvastatin coadministered with LY3314814 will represent the test treatment (Period 2 Day 8) for rosuvastatin PK analysis. PK parameter estimates will be evaluated to delineate the effects of LY3314814 on rosuvastatin PK.

Log-transformed AUC(0- ∞) and C_{\max} estimates for rosuvastatin will be analyzed using a linear mixed-effects analysis of variance model with treatment as a fixed effect and subject as a random effect. The ratios of geometric least squares (LS) means (ie, rosuvastatin + LY3314814 to rosuvastatin alone) will be calculated along with the 90% CI for the ratios.

The t_{\max} for rosuvastatin will be analyzed using a nonparametric method; median differences of rosuvastatin + LY3314814 to rosuvastatin alone and the 90% CI for the median of differences will be calculated.

Example SAS code:

```
proc mixed data=test covtest alpha=0.1;
  class treatment subject;
  model log_pk = treatment / ddfm=kr alpha=0.1;
  random subject;
  lsmeans treatment / pdiff cl alpha=0.1;
  ods output lsmeans=lsmeans;
  ods output diffs=diffs;
  ods output covparms=cov;
run;
```

A similar analysis will be performed on the secondary endpoints (LY3314814 AUC_τ, C_{\max} and t_{\max}) to evaluate the effect of rosuvastatin on LY3314814, where LY3314814 administered alone (Period 2 Day 7) will be the reference treatment and LY3314814 coadministered with rosuvastatin will remain the test treatment (Period 2 Day 8). Additional analysis may be conducted if deemed appropriate.

The effect of polymorphisms in genes coding for certain transporters (e.g., ABCG2, ABCB1, ABCC2, SLCO1B3, NTCP, and SLCO2B1) on the magnitude of the interaction between rosuvastatin and LY3314814 may be explored. For each subject, the ratio of rosuvastatin exposures with and without concomitant LY3314814 exposures will be calculated. A graphical analysis of these ratios between subjects with and without single nucleotide polymorphisms (SNPs) of interest is intended. Additional analyses may be conducted as warranted.

CCI

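### The SAP's between-profile outlier rule does not name the values it tests; on its natural reading it screens mostly between-subject variation, splits subject pairs, and should not decide the primary ratio

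*SAP*

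**What the plan says.** SAP 9.3.1, under the heading on data between individual profiles, applies with six or more values: "an objective outlier test will be used to compare the atypical value to other values included in that calculation". The steps are to take logs, then "Find the most extreme value from the arithmetic mean of the log transformed values and exclude that value from the dataset", then compute mean ± 3 SD of the remaining logs. A value outside that range is to be excluded, and the procedure may repeat. The set of values is not identified: treatment, period and subject ratio are not mentioned.

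The same section says the procedure need not be applied, does not oblige anyone to exclude a value, and will not remove complete profiles. Step e nevertheless says that an outlier will be excluded. Between profiles, results with and without the value are required only when there are fewer than six values. Exclusions are documented in the final report, and approving that report approves them.

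The primary analysis in SAP 9.3.2 is a "linear mixed-effects analysis of variance model with treatment as a fixed effect and subject as a random effect" on log AUC(0-∞) and Cmax. The ratio of geometric LS means "will be calculated along with the 90% CI for the ratios". Nothing is said about the partner value when one period's value has been removed.

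**The concern.** With one value per subject and treatment and a random subject effect, the primary result is in effect a within-subject ratio. A test that compares one subject's AUC with other subjects' AUCs works on a different scale. A subject who is high in both periods can be flagged although the ratio is ordinary. A profile that went wrong in one period can be hidden by the spread between subjects. Removing one period's value also leaves the other, often extreme as well, unpaired in the model. At stake is whether the primary ratio can be moved by deletions that have little to do with it, under a rule that is weak at finding the errors that do affect it.

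**Working it through.** **Inputs.**
- Completers: n = 24 (SAP 7: "Up to 28 subjects may be enrolled in order that 24 subjects complete the study"; Protocol 10.1, as amended, also plans for 24).
- AUC variability (Protocol 10.1): "the intrasubject variability (coefficient of variation) was estimated to be 25.5% by assuming intrasubject variability comprised half of the total variability of 51" percent. The alternative source "estimated the intrasubject variability of rosuvastatin AUC to be 21" percent.
- Confidence level 90% (SAP 9.3.2).
- Size of the error in a spoiled profile: not in the documents. It is an assumption, shown as a range from ×0.5 to ×0.1.

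**Log-scale SDs**, from σ² = ln(1 + CV²):
- Total: ln(1 + 0.51²) = 0.2312, SD 0.481.
- Within: ln(1 + 0.255²) = 0.0630, SD 0.251.
- Between: 0.2312 − 0.0630 = 0.1682, SD 0.410.
- Between-subject share, which is also the within-subject correlation: 0.1682/0.2312 = 0.73. With a 21% intrasubject CV it is 0.81.
- SD of the log ratio: √(2 × 0.0630) = 0.355.

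**The plan's own figure.** Protocol 10.1: "A sample size of 24 subjects will provide 92.3% probability that the estimated AUC geometric mean ratio will be within 0.15" of the 90% CI bounds on the log scale. P(half-width ≤ 0.15) = P(χ²_df ≤ df·[0.15/(t_0.95,df · 0.251 · √(2/24))]²) = 92.8% with df 23, or 92.2% with df 22. The stated 92.3% is reproduced, so these variances are the ones the plan used. For Cmax (CV 35.9%) the formula gives about 21%, against 19.6% stated.

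**Flag rate in clean data.** Per value: P(|t₂₂| > 3/√(1 + 1/23)) = 0.0076. Times 24, this is about 0.18 per dataset. Simulation gives 18% for one period and 31% for at least one of the two periods.

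**What is removed (clean data, intrasubject CV 25.5%).**
- In 88% of trials with a flag, the same subject is not flagged in both periods, so a pair is split (81% at CV 21%).
- Of the removed values, 85% belong to subjects whose log ratio is within 2 SD. Only 4% would be flagged on the ratio.
- The ratio moves by a median of 2.8% (95th percentile 6.0%), with mean shift near zero.
- 90% CI coverage falls from 90.2% to 89.4% over all trials, and to 87 to 88% in trials with a removal.

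**Detection of one spoiled test-period AUC (assumed factors, CV 25.5%).**

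| AUC multiplied by | One value per profile | Log ratio |
|---|---|---|
| 0.5 | 9% | 18–19% |
| 1/3 | 27–29% | 55% |
| 1/4 | 47% | 80% |
| 0.1 | 95% | over 99% |

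At CV 21% the log-ratio column is higher (94% at ×1/4). The advantage needs a correlation above 0.5. At exactly 0.5 the two tests are equal (47% each at ×1/4).

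**Cost of excluding on the ratio scale in the primary analysis (clean data).** An exclusion still occurs in 18% of trials. When it does, the ratio moves by a median of about 4%. Coverage is about 87 to 88% overall and about 76 to 77% in the trials affected.

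**Pair as the unit.** In clean trials with a flag on the present rule, dropping the whole pair instead of leaving the partner gives a median shift of 1.8% against 2.9%, root mean square error of 0.076 against 0.080, and coverage of 88.4% against 87.2%.

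**The case against.** The strongest reply has five parts.

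1. *The SAP does not say that the test is run on single-period exposures.* Correct. A reader might infer that it does, because the model takes one log value per subject and treatment, and subject ratios appear only in the exploratory genotype analysis. That is the natural reading but not a stated one. The firm defect in the text is that the dataset is undefined. Pooling all 48 values is another possible reading and gives a false flag in about 16 to 18% of trials.

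2. *The rule is optional and disclaims removing complete profiles.* Correct, so the 31% is an upper bound. But the rule is offered as justification for exclusion, step e is worded as mandatory, and removing a profile's AUC removes that profile from the primary model. These sentences need reconciling.

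3. *Known errors have other routes.* SAP 8 allows exclusion for early vomiting and takes protocol deviations into account when populations are assigned. That narrows the need for the rule and supports relying on documented causes.

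4. *Testing and excluding on the ratio would do more harm.* This stands for the primary analysis: it trims the scale of the estimand and costs more coverage than the present rule. It does not count against using the ratio as a screen for sensitivity analysis.

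5. *The 73% is soft.* The intrasubject CV is assumed to be half the total, and genotype exclusions may narrow the spread between subjects. This stands as a caveat. The documents' two intrasubject CVs, with the 51% total, give 0.73 to 0.81, well above the 0.5 at which the advantage vanishes.

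**Conclusion.** The point holds in a limited form. The rule leaves its dataset undefined. On the natural reading it screens variation that the primary model already removes, splits most of the pairs it touches, and detects three- to fourfold errors a little more than half as often as a log-ratio screen.

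The effect on the primary result is modest: a median shift of about 3% when a value is removed, against a planned half-width of about 16% (exp(0.15) − 1 = 0.162), and a loss of under one percentage point of coverage over all trials.

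A reader might go further and conclude that the rule generally removes harmless values and misses spoiled profiles. That is not supported. In clean data most removed values do have ordinary ratios, but a tenfold loss is caught 95% of the time, at ×1/4 the spoiled value is flagged more often than good ones (47% against about 23% over both periods), and even the log-ratio test misses about 82% of twofold losses.

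The figures assume log-normal data, 24 complete pairs, the plan's CVs, automatic use of the rule on AUC, and error sizes that are not in the documents. This should be corrected, but it does not invalidate the primary analysis.

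**What to change.** Amend SAP 9.3.1 and cross-refer to it from 9.3.2:

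1. Keep all values in the primary mixed-model analysis unless there is a documented cause, such as vomiting, or a dosing, sampling or assay error.
2. Name the dataset tested. For AUC and Cmax, run the step 2 screen on each subject's log(test/reference) or on model residuals. Report any purely statistical exclusion as a sensitivity analysis only.
3. Where a value is excluded, treat the subject's pair as the unit, so that no extreme partner value stays in the model unpaired.
4. Reconcile the sentence making exclusion optional with step e, and the sentence on complete profiles with removal of a profile's AUC or Cmax.

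The cost is SAP wording, a small programming change and one extra analysis when something is flagged. The SAP already foresees subject-level ratios of rosuvastatin exposure for the genotype work. The downside is that extreme values with no identified cause stay in the primary result, where the sensitivity analysis shows their influence.

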8. DEFINITION OF ANALYSIS POPULATIONS

The “Safety” population will consist of all enrolled subjects, whether or not they completed all protocol requirements.

The PK analyses will be conducted on the “Full analysis set”. This set includes all data from all subjects who received at least one dose of study drug and have evaluable PK data. Subjects may be excluded from the PK summary statistics and statistical analysis if a subject has an AE of vomiting that occurs at or before 2 times median time to maximum concentration (t_{max}).

Additional exploratory analyses of the data will be conducted as deemed appropriate. Study results may be pooled with the results of other studies for population PK analysis purposes to avoid issues with post-hoc analyses and incomplete disclosures of analyses.

All protocol deviations that occur during the study will be considered for their severity/impact and will be taken into consideration when subjects are assigned to analysis populations.

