9. STATISTICAL METHODOLOGY

9.1 General

Data listings will be provided for all data that is databased. Summary statistics and statistical analysis will only be presented for data where detailed in this SAP. For continuous data, summary statistics will include the arithmetic mean, arithmetic standard deviation (SD), median, min, max and N; for log-normal data (e.g. the PK parameters: AUCs and C_{max}) the geometric mean and geometric CV% will also be presented. For categorical data, frequency count and percentages will be presented. Data listings will be provided for all subjects up to the point of withdrawal, with any subjects excluded from the relevant population highlighted. Summary statistics and statistical analyses will generally only be performed for subjects included in the relevant analysis population. For the calculation of summary statistics and statistical analysis, unrounded data will be used.

Mean change from baseline is the mean of all individual subjects' change from baseline values. Each individual change from baseline will be calculated by subtracting the individual subject's

baseline value from the value at the timepoint. The individual subject's change from baseline values will be used to calculate the mean change from baseline using a SAS procedure such as Proc Univariate.

Data analysis will be performed using SAS® Version 9.3 or greater.

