9.3 Pharmacokinetic Assessment

9.3.1 Pharmacokinetic Analysis

PK parameter estimates will be determined using non-compartmental procedures in validated software program (Phoenix WinNonlin Version 6.4.1 or later).

Plasma concentrations of rosuvastatin will be used to determine the following PK parameters, when possible:

Parameter	Units	Definition
AUC(0-t _{last})	ng.h/mL	area under the concentration versus time curve from time zero to time t, where t is the last time point with a measurable concentration
AUC(0-∞)	ng.h/mL	area under the concentration versus time curve from zero to infinity
%AUC(t _{last} -∞)	%	percentage of AUC(0-∞) extrapolated
C _{max}	ng/mL	maximum observed drug concentration
t _{max}	h	time of maximum observed drug concentration
t _{1/2}	h	half-life associated with the terminal rate constant (λ _z) in non-compartmental analysis
CL/F	L/h	apparent total body clearance of drug calculated after extra-vascular administration
V _z /F	L	apparent volume of distribution during the terminal phase after extra-vascular administration
V _{ss} /F	L	apparent volume of distribution at steady state after extra-vascular administration

An alternative AUC measure, such as AUC to a common time point, may be calculated if AUC(0-∞) cannot be reliably calculated.

Plasma concentrations of LY3314814 will be used to determine the following PK parameters, when possible:

Parameter	Units	Definition
$AUC_{\tau, ss}$	ng.h/mL	area under the concentration versus time curve during one dosing interval at steady state
$C_{max, ss}$	ng/mL	maximum observed drug concentration at steady state
$t_{max, ss}$	h	time of maximum observed drug concentration at steady state
CL_{ss}/F	L/h	apparent total body clearance of drug calculated after extra-vascular administration at steady state

Additional PK parameters may be calculated, as appropriate. The software and version used for the final analyses will be specified in the CSR. Any exceptions or special handling of data will be clearly documented within the final study report.

Formatting of tables, figures and abbreviations will follow the Eli Lilly Global PK/PD/TS Tool: NON-COMPARTMENTAL PHARMACOKINETIC STYLE GUIDE. The version of the tool effective at the time of PK analysis will be followed.

General PK Parameter Rules

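### The SAP's outlier rule says both that exclusion is optional and that it will happen, and with 24 subjects it promises no 90% CI from all values

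*SAP*

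**What the plan says.** The rule is in SAP 9.3.1, under Treatment of Outliers during Pharmacokinetic Analysis.

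- **Preamble.** The procedure need not be used in every PK analysis. It identifies values that might be excluded, but it "does not require that the value be excluded from analysis". It adds: "The following methodology will not be used to exclude complete profiles from analysis".
- **Between profiles, n < 6.** "Data will be analyzed with and without the atypical value, and both sets of results will be reported".
- **Between profiles, n ≥ 6.** If n is 6 or more, "then an objective outlier test will be used to compare the atypical value to other values included in that calculation". Values are logged, the most extreme is set aside, and limits of mean ± 3 SD are computed from the rest. Under step 2e, if the value lies outside them, "then it is an outlier and will be excluded from analysis". The test may be repeated, one value at a time, while n is at least 6.
- **Reporting.** Excluded values are to be documented in the final report, and approval of that report counts as approval of the exclusion. Elsewhere in 9.3.1, an AUC(0-∞) value left out of the summary statistics gets a table footnote, and "Any exceptions or special handling of data will be clearly documented within the final study report". SAP 9.1 promises listings: "Data listings will be provided for all subjects up to the point of withdrawal, with any subjects excluded from the relevant population highlighted".
- **Analysis set (SAP 8).** "This set includes all data from all subjects who received at least one dose of study drug and have evaluable PK data".
- **Primary model (SAP 9.3.2).** A mixed model on log AUC(0-∞) and Cmax gives the ratio and its 90% CI. The section has no outlier provision and no sensitivity analysis.

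**The concern.** Once a value has been identified as an outlier, the preamble leaves its exclusion open and step 2e makes it certain. Two analysts with the same flagged value could report different primary results, and each could cite the SAP.

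The n ≥ 6 branch is the one that applies here, and it is the branch without dual reporting. A deletion would be documented, but a reader who wanted the all-values 90% CI would have to recompute it from the listings. The study is open-label and the exclusion is endorsed by approving the report, so the decision comes after the data are seen.

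Scope is also unclear. Values in a calculation, compared between profiles on the log scale, could well be derived AUC(0-∞) or Cmax values. The ban on excluding complete profiles points the other way. If derived values are in scope, the rule can remove a subject's primary-endpoint value from a set that SAP 8 describes as all data.

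**Working it through.** **1. The text.** The SAP promises results both with and without a value in two places: between profiles for n < 6, and for a questionable datum inside one profile. The second concerns single concentrations, so it does not cover a subject-level AUC or Cmax. Steps 2a to 2e, the reporting paragraph, SAP 8, 9.1 and 9.3.2, and the footnote rule promise listings, documentation or footnotes. None promises a second CI.

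**2. Inputs.** Protocol 10.1 and SAP 7 give 24 completers, AUC CV 25.5% within subject and 51% total, an alternative within-subject AUC CV of 21%, and Cmax CV 35.9% and 71.8%. On the log scale, s = √ln(1 + CV²). For AUC this is 0.251 within subject and 0.481 total.

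**3. The plan's own precision figure.** CI half-width = t(0.95, 23) × s_w × √(2/24) = 1.714 × 0.251 × 0.2887 = 0.124. With s_w² estimated on 23 df, the probability that the half-width is at most 0.15 is 92.8%. Conditional on the CI covering the true ratio it is 92.4% (simulation). The plan states 92.3%. For Cmax the conditional figure is 19.5%, against 19.6% stated. The inputs are therefore read as the plan intended.

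**4. How tight the limit is at n = 24.** The tested value is left out of the SD.

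- Leave-one-out rule: P(|t₂₂| > 3/√(1 + 1/23)) = P(|t₂₂| > 2.937) = 0.00763 per value. Times 24, this is 0.183 per treatment.
- 3 SD with the value left in: B = 9 × 24/23² = 0.408; t = √(22B/(1 − B)) = 3.90; P = 0.00078 per value. Times 24, this is 0.019.
- Equivalent limit with the value left in: t² = 9/(1 + 1/23) = 8.625; B = 8.625/(22 + 8.625) = 0.2816; √(B × 23²/24) = 2.49 SD.

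**5. Effect on the 90% CI.** The iterative rule was simulated on clean log-normal data, separately for each rosuvastatin treatment, always testing the most extreme value. After deletion, the analysis was either a REML mixed model (df = complete pairs − 1, approximating Kenward-Roger) or complete pairs only.

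| | AUC, CV 25.5% | AUC, CV 21% | Cmax, CV 35.9% |
|---|---|---|---|
| Runs | 20,000 | 12,000 | 12,000 |
| Trials losing at least one value | 30.7% | 30.5% | 31.3% |
| Coverage in affected trials: untrimmed | 90.4% | 90.1% | 90.1% |
| – mixed model | 87.1% | 88.0% | 87.0% |
| – complete pairs | 88.4% | 89.1% | 88.5% |
| Mean absolute log shift: mixed model | 0.0307 | 0.0229 | 0.0428 |
| – complete pairs | 0.0203 | 0.0156 | 0.0284 |

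For AUC at CV 25.5%:

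- Coverage over all trials is 89.4% (mixed model) or 89.8% (pairs), against 90.4% untrimmed.
- The 95th percentile of the shift is 0.062 or 0.045 log units. The mean signed shift is −0.0003, so there is no bias in direction.
- The mean shift of 0.0307 is a quarter of the mean untrimmed half-width: 0.0307/0.123 = 0.25.
- The Monte Carlo standard error of coverage in the 6,144 affected trials is 0.004.

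A separate simulation with complete pairs gave 31.1% of trials affected and overall coverage of 89.7% against 90.3%.

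**The case against.** The strongest reply has four parts.

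1. **The wording can be partly reconciled.** Step 2e sits inside a procedure whose use is optional. That explains the sentence about applying the procedure. It does not explain the sentence saying that an identified value need not be excluded, so the conflict stands once the test has been run.
2. **The primary endpoint may be out of scope.** The procedure names neither AUC(0-∞) nor the model. Deleting one period's AUC comes close to excluding a complete profile, and the preceding rules concern averages of concentrations at a time point. This is a fair reading, and on it the effect on the primary result is nil. The SAP does not settle the matter.
3. **The rates overstate use.** The text starts from a value that already looks atypical and allows exclusion only where scientifically appropriate. On the per-treatment scale at the planning SD, the limit is about exp(3 × 0.481) = 4.2-fold from the geometric mean. This stands: 18% and 31% are upper bounds, and the documents give no basis for a realistic rate.
4. **The effect is small and visible.** There is no mean bias and no pre-set no-effect boundary to cross. Exclusions are documented, and the all-values CI can be recomputed from listings. The planned tables are in a TFL shell document that is not available here. SAP 8 also allows exclusion for vomiting, so its reference to all data is not absolute. All of this limits the weight of the point. It does not supply the missing CI.

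**Conclusion.** The concern holds. SAP 9.3.1 contradicts itself about an identified outlier, and for n ≥ 6 it promises no all-values 90% CI beside a trimmed one.

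The size depends on scope. If derived parameters are out of scope, or nothing is deleted, there is no effect. If they are in scope and the extreme value is always tested, the rule deletes valid values in up to about 31% of trials with clean log-normal data. In those trials, AUC coverage at CV 25.5% falls by about 2 to 3 points. The ratio moves by about 3% (mixed model) or 2% (pairs) on average, in either direction. That is small beside the increase of about 70% anticipated in Protocol 5.5, so the main conclusion would be unlikely to change.

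The point should still be corrected. The primary analysis should be reproducible from the SAP, and valid primary-endpoint values should not be removable after the data are seen without the full result being shown.

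**What to change.** - In step 2e, replace exclusion with flagging, so that it agrees with the preamble.
- State that the primary 90% CI uses all evaluable values.
- When a value is flagged, report the analysis without it beside the primary result as a sensitivity analysis. This extends the SAP's own n < 6 practice to n ≥ 6.
- State whether derived AUC and Cmax values are within the procedure, and how that fits with the sentence on complete profiles.

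The cost is a few lines of SAP text, and one extra model run only when a value is flagged.
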